Appendix 4 Short Form 12 Health Survey (SF-12)

SF-12 Health Survey

This survey asks for your views about your health. This information will help keep track of how you feel and how well you are able to do your usual activities. Answer each question by choosing just one answer. If you are unsure how to answer a question, please give the best answer you can.

1. In general, would you say your health is:

₁ Excellent ₂ Very good ₃ Good ₄ Fair ₅ Poor

The following questions are about activities you might do during a typical day. Does your health now limit you in these activities? If so, how much?

	YES, limited a lot	YES, limited a little	NO, not limited at all
2. Moderate activities such as moving a table, pushing a vacuum cleaner, bowling, or playing golf.	 ₁	 ₂	 ₃
3. Climbing several flights of stairs.	 ₁	 ₂	 ₃

During the past 4 weeks, have you had any of the following problems with your work or other regular daily activities as a result of your physical health?

	YES	NO
4. Accomplished less than you would like.	 ₁	 ₂
5. Were limited in the kind of work or other activities.	 ₁	 ₂

During the past 4 weeks, have you had any of the following problems with your work or other regular daily activities as a result of any emotional problems (such as feeling depressed or anxious)?

	YES	NO
6. Accomplished less than you would like.	 ₁	 ₂
7. Did work or activities less carefully than usual.	 ₁	 ₂

8. During the past 4 weeks, how much did pain interfere with your normal work (including work outside the home and housework)?

₁ Not at all ₂ A little bit ₃ Moderately ₄ Quite a bit ₅ Extremely

These questions are about how you have been feeling during the past 4 weeks.

For each question, please give the one answer that comes closest to the way you have been feeling.

How much of the time during the past 4 weeks...

	All of the time	Most of the time	A good bit of the time	Some of the time	A little of the time	None of the time
9. Have you felt calm & peaceful?	 ₁	 ₂	 ₃	 ₄	 ₅	 ₆
10. Did you have a lot of energy?	 ₁	 ₂	 ₃	 ₄	 ₅	 ₆
11. Have you felt down-hearted and blue?	 ₁	 ₂	 ₃	 ₄	 ₅	 ₆

12. During the past 4 weeks, how much of the time has your physical health or emotional problems interfered with your social activities (like visiting friends, relatives, etc.)?

₁ All of the time ₂ Most of the time ₃ Some of the time ₄ A little of the time ₅ None of the time

Patient name:	Date:	PCS:	MCS:
Visit type (circle one)			
Preop	6 week	3 month	6 month
		12 month	24 month
			Other: _____

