7.2 Secondary Endpoints

7.2.1 Efficacy

Per the protocol, the secondary efficacy endpoints are:

- To determine the number of subjects with subsequent prostate cancer treatment (e.g., surgery, radiation, ADT) in each study arm
- Characterization of PROs by Memorial Anxiety Scale for Prostate Cancer (MAX-PC), Short Form 12 Health Survey (SF-12), The Expanded Prostate Cancer Index Composite for Clinical Practice (EPIC-CP), and International Prostate Symptom Score (IPSS) at baseline and 12-, 24-, and 36-month visits after randomization

The interpretations of these secondary efficacy endpoints based on the objectives, as assessed from baseline at the 12, 24, and 36 months visits post randomization, are as follows:

- Subsequent Prostate Cancer Treatment
 - Proportions of subjects with subsequent prostate cancer treatment
 - Time to the First Subsequent Prostate Cancer Treatment
- Patient Reported Outcomes (PROs). Will assess PROs at each collection point including change from baseline in the
 - MAX-PC total score and subscores for Prostate Cancer Anxiety, PSA Anxiety, and Fear of Recurrence,
 - SF-12 domain and QOL score and the SF-6D Quality adjusted Life Years index
 - EPIC-CP overall response and individual and pooled domain scores, and
 - I-PSS total scores, each of the urinary symptoms scores, and the quality of life due to urinary symptoms score.

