8.1.3.2 Short Form 12 Health Survey (SF-12)

The Standard SF-12 ([Appendix 4](#)) captures the subject's views about their own functional health and well-being in the past 4 weeks in 12 items. There are eight health domains measured using the SF-12 as follows:

- General Health (GH) – question 1 with a range of 1-5
- Physical Functioning (PF) – questions 2 and 3 with a range of 1-3 each
- Role-Physical (RP) – questions 4 and 5 with a range of 1-2 each
- Role-Emotional (RE) – questions 6 and 7 with a range of 1-2 each
- Bodily Pain (BP) – question 8 with a range of 1-5
- Mental Health (MH) – questions 9 and 11 with a range of 1-6 each
- Vitality (VT) – question 10 with a range of 1-6
- Social Functioning (SF) – question 12 with a range of 1-5

The SF-12 responses will be scored using OPTUM® PRO CoRE software, version 1.4 or higher, producing scores for the 8 health domains and the physical component summary (PCS) and mental component summary (MCS). Higher scores reflect higher functioning and well-being. The SF-6D index, a health state classification measure scored from 0.0 (worst health state) to 1.0 (best health state), will be derived based on the SF-12.

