12.6.2.2 PROs

For each PRO total score and pooled domain score or sub-score defined in [Section 8.1.3](#), actual values at baseline and change from baseline at 12, 24, and 36 months visits post randomization will be summarized in the ITT and PP analysis sets in each treatment arm. The best change within 36 months post-baseline will be summarized and compared between the arms. The responses to individual question items will not be summarized except for the EPIC-CP overall urinary function question, which will be presented at baseline and its shift change presented at post-randomization.

To assess potential missing individual items in each PRO questionnaire, a sensitivity analysis in the ITT analysis set will be conducted to calculate total scores and pooled domain scores by summing up all available individual items regardless of any missing individual score.

PRO results will be provided in a listing.

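### Read literally, the PRO sensitivity analysis adds SF-12 item codes that run in opposite directions, so the Mental Health domain is 7 at both best and worst health (minor)

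*SAP*

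**What the plan says.** SAP 7.2.1 makes four PRO instruments a secondary efficacy endpoint: MAX-PC, SF-12, EPIC-CP and I-PSS. SAP 12.6.2.2 sets the missing-item analysis: "To assess potential missing individual items in each PRO questionnaire, a sensitivity analysis in the ITT analysis set will be conducted". Its method is to "calculate total scores and pooled domain scores by summing up all available individual items regardless of any missing individual score". No instrument is exempted. The SAP gives no rule for reversing, recoding or prorating items.

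SAP 8.1.3.2 treats SF-12 differently from the other three: "The SF-12 responses will be scored using OPTUM® PRO CoRE software, version 1.4 or higher". The output is eight domain scores plus the physical and mental component summaries, and "Higher scores reflect higher functioning and well-being". The section assigns items and code ranges to domains; Mental Health is items 9 and 11, each coded 1 to 6. It defines no 12-item total and gives no missing-item rule for SF-12.

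SAP Appendix 4 prints the form. Item 1 is coded "₁ Excellent ₂ Very good ₃ Good ₄ Fair ₅ Poor". Items "9. Have you felt calm & peaceful" and "11. Have you felt down-hearted and blue" share one set of response columns, from all of the time (1) to none of the time (6).

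**The concern.** A sum of items means something only if all the items point the same way. On the SF-12 form they do not. If the rule in 12.6.2.2 is applied to SF-12 as it stands, a positively worded and a negatively worded item are added with the same sign, and the answers offset each other.

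This is separate from how blanks are treated. It happens on a fully completed form, so prorating for missing items would not cure it. At stake is whether the SF-12 part of the sensitivity analysis can be read at all. A difference between it and the main SF-12 result could come from item coding alone and say nothing about missing items.

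**Working it through.** **Inputs.** Item codes come from the form in SAP Appendix 4. Domain membership and direction come from SAP 8.1.3.2. The SAP states no SF-12 item sum, so there is no figure to reproduce. As a check on the inputs, the item ranges in 8.1.3.2 match the printed form, and the maxima stated for the other instruments follow by addition: MAX-PC 18 × 3 = 54, EPIC-CP 5 × 12 = 60, I-PSS 7 × 5 = 35.

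**Direction of each item.** Code 1 is the best answer for items 1, 8, 9 and 10. Code 1 is the worst answer for items 2 to 7, 11 and 12.

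**Sum of printed codes by domain.**

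| Domain | Items | Best health | Worst health | A high value means |
|---|---|---|---|---|
| General Health | 1 | 1 | 5 | worse |
| Physical Functioning | 2, 3 | 3 + 3 = 6 | 1 + 1 = 2 | better |
| Role-Physical | 4, 5 | 2 + 2 = 4 | 1 + 1 = 2 | better |
| Role-Emotional | 6, 7 | 2 + 2 = 4 | 1 + 1 = 2 | better |
| Bodily Pain | 8 | 1 | 5 | worse |
| Mental Health | 9, 11 | 1 + 6 = 7 | 6 + 1 = 7 | neither |
| Vitality | 10 | 1 | 6 | worse |
| Social Functioning | 12 | 5 | 1 | better |

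**Mental Health between the extremes.** If a subject's two answers mirror each other, item 9 is coded k and item 11 is coded 7 − k. The sum is k + (7 − k) = 7 for every k from 1 to 6. The sum leaves 7 only when the two answers disagree. It is 1 + 1 = 2 for always calm and always down-hearted, and 6 + 6 = 12 for never either. With item 9 reversed (7 − code), best health gives 6 + 6 = 12 and worst gives 1 + 1 = 2.

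**Mental Health with one item blank**, which is the case the analysis is meant for. If item 11 is blank, the sum of available items is 1 at best and 6 at worst. If item 9 is blank, it is 6 at best and 1 at worst. The direction of the score then depends on which item was skipped.

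**All twelve items**, a score the SAP does not define:
- Best: 1+3+3+2+2+2+2+1+1+1+6+5 = 29.
- Worst: 5+1+1+1+1+1+1+5+6+6+1+1 = 30.
- The possible range is 12 to 47.

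**Would reversal be enough?** With items 1, 8, 9 and 10 reversed, the total is 47 at best and 12 at worst. A perfect-health form with item 9 or item 11 blank would still fall to 47 − 6 = 41. The result would also still be a sum of codes, not a software score.

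**MAX-PC check.** The form in SAP Appendix 3 codes items 15 to 18, all statements of worry, from 0 for strong agreement to 3 for strong disagreement. SAP 8.1.3.1 says higher is worse. Adding the printed codes, a man with no anxiety scores 14 × 0 + 4 × 3 = 12, and a man with the most scores 14 × 3 + 4 × 0 = 42, on a stated range of 0 to 54.

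**The case against.** The best reply is that the sponsor never meant to sum SF-12. The score types named in the rule, totals and pooled domain scores, fit the other three instruments. SAP 7.2.1 speaks of pooled domain scores for EPIC-CP only. The rule being relaxed, under which one missing item makes the score missing, appears in 8.1.3.1, 8.1.3.3 and 8.1.3.4 but not in 8.1.3.2. On this view the word *each* is loose drafting. The table shells cited in SAP Appendix 2, which might settle the matter, are not among the documents.

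Much of this stands, and the narrower reading is plausible. But the text says each questionnaire and limits nothing. Because 8.1.3.2 has no missing-item rule of its own, 12.6.2.2 is the only one a programmer could apply to SF-12. A programmer might recode the items first, but the SAP gives no such instruction.

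A reader might also infer that summing reverses three of the eight domains. General Health, Bodily Pain and Vitality have one item each, so nothing is summed. Their printed codes run against the stated direction, but the rule does no missing-item work there. Mental Health is the only domain where adding the items cancels the signal.

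**Conclusion.** The point holds as a minor defect of scope. Taken at its word, 12.6.2.2 produces an SF-12 Mental Health sum that cannot tell best from worst health (7 and 7), three single-item codes that run against the SAP's stated direction, and no value on the scale of the software scores. This rests on two assumptions: that *each* includes SF-12, and that the printed codes are summed without recoding.

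Two stronger readings are tempting. The first is that the SAP produces an SF-12 total of 29 for perfect health and 30 for the worst. The addition is right, but the SAP names no such total; the Mental Health result needs only a domain that it does define. The second is that a real SF-12 benefit would vanish, or that the trial's conclusion is at risk. The documents state no expected SF-12 effect, so any figure for a lost difference between arms would rest on assumptions from outside them. The software-scored SF-12 analysis is untouched, and under SAP 12.6.1.2 the success of the study rests on one test of the primary endpoint.

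**What to change.** - In SAP 12.6.2.2, limit the sum-of-items sensitivity analysis to MAX-PC, EPIC-CP and I-PSS, and exclude SF-12 and SF-6D by name.
- For SF-12, handle missing items within the scoring software named in 8.1.3.2, or analyse complete forms only, so that scores keep the scale and direction of the main analysis.
- Before MAX-PC is summed, reconcile the printed coding of items 15 to 18 with the direction stated in 8.1.3.1. This is a separate matter that also bears on the main MAX-PC score, so MAX-PC should not be taken as safe to sum until it is settled.

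The SF-12 change costs one sentence and needs no new data. The downside is that the SF-12 sensitivity analysis will depend on what the software offers, or will be confined to complete forms.

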Appendix 5 The Expanded Prostate Cancer Index Composite for Clinical Practice (EPIC-CP)

Expanded Prostate Cancer Index Composite for Clinical Practice (EPIC-CP) Prostate Cancer Quality of Life (QOL)

Patient Name: _____ Date of Birth: _____

Physician: _____ Date of Visit: _____

Patients: Please answer the following questions by circling the appropriate answer. All questions are about your health and symptoms in the **LAST FOUR WEEKS**.

Select ONE answer for each question:

1. Overall, how much of a problem has your urinary function been for you?				
No Problem	Very small problem	Small problem	Moderate problem	Big problem

2. Which of the following best describes your urinary control?				
0-Total control	1-Occasional dribbling	2-Frequent dribbling	3-Moderate urinary control	4- No urinary control

3. How many pads or adult diapers per day have you been using for urinary leakage?				
0-None	1-One pad per Day	2-Two pads per Day	3-Three pads per Day	4- Three or more pads

4. How big a problem, if any has urinary dripping or leakage been for you?				
0-No problem	1-Very small problem	2-Small problem	3-Moderate problem	4-Big problem

CLINICIANS: Add the answers from questions 2-4 to calculate the **Urinary Incontinence Symptom Score (out of 12)**

5. How big a problem, if any, has each of the following been for you?					
	No problem	Very small problem	Small problem	Moderate problem	Big problem

a. Pain or burning with urination	0	1	2	3	4
-----------------------------------	---	---	---	---	---

b. Weak urine stream/incomplete bladder emptying	0	1	2	3	4
--	---	---	---	---	---

c. Need to urinate frequently	0	1	2	3	4
-------------------------------	---	---	---	---	---

CLINICIANS: ADD the answers from questions 5a-5c to calculate the **Urinary Irritation/Obstructive Symptom Score (out of 12)**

6. How big a problem, if any, has each of the following been for you?					
	No problem	Very small problem	Small problem	Moderate problem	Big problem

a. Rectal pain or urgency of bowel movements	0	1	2	3	4
--	---	---	---	---	---

b. Increased frequency of your bowel movements	0	1	2	3	4
--	---	---	---	---	---

c. Overall problems with your bowel movements	0	1	2	3	4
---	---	---	---	---	---

CLINICIANS: ADD the answers from questions 6a-6c to calculate the **Bowel Symptom Score (out of 12)**

7. How do you rate your ability to reach orgasm (climax)?				
0- Very good	1-Good	2-Fair	3-Poor	4-Very poor to none

8. How would you describe the usual quality of your erections?			
0- Firm enough for intercourse	1-firm enough for masturbation and foreplay	2-Not firm enough for any sexual activity	4-None at all

9. Overall, how much of a problem has your sexual function or lack of sexual function been for you?				
0-No problem	1-Very small problem	2-Small problem	3-Moderate problem	4-Big problem

10. How big a problem, if any, has each of the following been for you?					
	No problem	Very small problem	Small problem	Moderate problem	Big problem

a. Hot flashes or breast tenderness/enlargement	0	1	2	3	4
---	---	---	---	---	---

b. Feeling depressed	0	1	2	3	4
----------------------	---	---	---	---	---

c. Lack of energy	0	1	2	3	4
-------------------	---	---	---	---	---

CLINICIANS: ADD the answers from question s10a-10c to calculate the **Vitality/Hormonal Symptom Score(out of 12)**

CLINICIANS: ADD the five domain summary scores to calculate the **Overall Prostate Cancer QOL Score (out of 60)**

Appendix 6 International Prostate Symptom Score (I-PSS)

International Prostate Symptom Score (I-PSS)

Patient Name: _____ Date of birth: _____ Date completed _____

In the past month:	Not at All	Less than 1 in 5 Times	Less than Half the Time	About Half the Time	More than Half the Time	Almost Always	Your score
1. Incomplete Emptying How often have you had the sensation of not emptying your bladder?	0	1	2	3	4	5	
2. Frequency How often have you had to urinate less than every two hours?	0	1	2	3	4	5	
3. Intermittency How often have you found you stopped and started again several times when you urinated?	0	1	2	3	4	5	
4. Urgency How often have you found it difficult to postpone urination?	0	1	2	3	4	5	
5. Weak Stream How often have you had a weak urinary stream?	0	1	2	3	4	5	
6. Straining How often have you had to strain to start urination?	0	1	2	3	4	5	
	None	1 Time	2 Times	3 Times	4 Times	5 Times	
7. Nocturia How many times did you typically get up at night to urinate?	0	1	2	3	4	5	
Total I-PSS Score							

Score: 1-7: *Mild* 8-19: *Moderate* 20-35: *Severe*

Quality of Life Due to Urinary Symptoms	Delighted	Pleased	Mostly Satisfied	Mixed	Mostly Dissatisfied	Unhappy	Terrible
If you were to spend the rest of your life with your urinary condition just the way it is now, how would you feel about that?	0	1	2	3	4	5	6

Appendix 7 Eastern Cooperative Oncology Group (ECOG) Performance Status

Grade	Performance Criteria	Karnofsky Scale Equivalent
0	Normal activity. Fully active, able to carry on all predisease performance without restriction.	90-100
1	Symptoms but ambulatory. Restricted in physically strenuous activity but ambulatory and able to carry out work of a light or sedentary nature (e.g., light housework, office work).	70-80
2	In bed < 50% of the time. Ambulatory and capable of self-care, but unable to carry out any work activities. Up and about more than 50% of waking hours.	50-60
3	In bed > 50% of the time. Capable of only limited self-care, confined to bed or chair more than 50% of waking hours.	30-40
4	100% bedridden. Completely disabled. Cannot carry on any self-care. Totally confined to bed or chair.	10-20
5	Dead	0
